#### **2.4.2 Prior, concomitant and post therapies**

Prior or concomitant medications will be summarized for the safety set in separate tabulations based on the coding dictionary used. Prior and concomitant medications used during the randomized phase will be summarized by therapeutic class, preferred term and treatment group.

The SAF population will be used for the above analyses.

Prior medications are defined as drugs taken prior to index hospital admission. Concomitant medication is any medication given at least once post-admission and the last day of the study, including those which were started pre-admission and continued post-admission. Prior or concomitant medication will be identified based on recorded or imputed start and end dates of medication taking. Medications administered during the acute treatments of the decompensated heart failure event (from admission to the time of signing ICF) will NOT be included in the CRFs. Concomitant medication at discharge will be summarized separately.

Per protocol, HF-related therapy starting after the End of Study (to ensure adequate chronic treatment after conclusion of study participation) is also reported. This therapy is HF-specific and may start either on the same day of EoS or as late as 10 days later due to availability in the country of the commercial product, and also considering the needed 36-h washout that may be

needed to resume ACEI treatment after ending study medication administration. A separate table will be compiled indicating the treatment started after End of study Visit.

Prior and concomitant heart failure and cardiovascular-related medications will be summarized separately at separate time points. To be consistent with LCZ696B2314, here are the medications that will be summarized:

- ACEi\*
- ARBs\*
- Beta-blocking agents\*
- Diuretic\*
- Loop diuretics
- Thiazide
- Other Potassium sparing diuretics
- Mineralocorticoid receptor antagonists (MRAs)\*
- Digoxin
- Cardiac glycosides\*
- Calcium Channel Blockers (CCB)/Calcium antagonist\*
- Nitrates\*
- Other vasodilators\*
- Oral anticoagulant\*
- Other antiplatelet agents\*
- Aspirin\*
- Antiarrhythmic agent\*
- Statins\*
- Other lipid lowering agents\*
- Simvastatin
- Inotropic agents

Note: those with an asterisk will be included additionally in a figure

The classes of medications will be defined in a separate file with ATC preferred term and WHO drug code.

The compliance with 36-hour washout from ACEi strata will also be summarized.

## **2.5 Analysis of the primary objective**

### **2.5.1 Primary endpoint**

The primary variable is 10 weeks up-titration success, and is defined as: “achieving the target dose of LCZ696 200 mg bid at 10 weeks after randomization (Visit 199) regardless of previous dose interruption or down-titration (Yes/no)”. There is no primary efficacy analysis. The Safety Population (SAF) will be used for the primary endpoint analysis. The primary endpoint will also be investigated for its robustness across subgroups defined in section 2.2.1.

### **2.5.2 Statistical hypothesis, model, and method of analysis**

The primary endpoint will be analyzed using the stratified Cochran-Mantel-Haenszel method with treatment group and randomization stratification variable (ACEI stratum, ARB stratum, or naïve patient stratum) as stratification factor; although randomization is stratified at the country level, country will not be used here as an additional stratification factor due to the expected small cell counts in some countries, in particular in the naïve patient stratum. The risk ratio (of the Pre-discharge initiation of LCZ696 arm versus the Post-discharge initiation of LCZ696 arm) will be estimated with a 2-sided 95% CI along with the estimated rate and 95% CI for each treatment arm. The above analyses will be performed based on SAF; patients will be analyzed according to treatment actually received, as well as the actual stratum (rather than randomized stratum).

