9.1 Analysis sets

The following populations will be used for the statistical analyses:

Randomized Population (RAN) will consist of all patients randomized.

The full analysis set (FAS) will consist of all randomized patients with the exception of those patients who have not received study drug, but have been inadvertently randomized into the study. Following the intent-to-treat principle, patients will be analyzed according to the treatment to which they were assigned at randomization.

The Safety Population (SAF) will consist of all randomized patients who received at least one dose of study drug. Patients will be analyzed according to treatment actually received. The safety population will be used for the analyses of safety variables.

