### Document History – Changes compared to previous final version of SAP

Date	Time point	Reason for update	Outcome for update	Section and title impacted (Current)
04-MAR-2016	Prior to DB lock	Creation of final version	First version	NA
10-Nov-2017	Prior to DB lock	Add SCR set Update the rehospitalization not-HF cause Update concomitant medication selection and imputation rules on dates Update the exposure cutoff to be consistent with protocol visit window Add liver toxicity criteria table and notable vital sign criteria Update PDs that excluded from populations Detail liver and renal events	Amendment 1	NA
16-Mar-2018	Prior to DB lock	Typology updates FAS/SAF definitions Update compliance information Update prior/concomitant definitions Update TEAE definition Update concomitant medication start date imputation rules on date	Amendment 2	NA
17-Apr-2018	Prior to DB lock	Add Protocol deviation OTH13: Patient not starting	Amendment 3	NA

Date	Time point	Reason for update	Outcome for update	Section and title impacted (Current)
		
treatment within protocol specified windows. Patients with this PD to be excluded from FAS and included in SAF.
 
Definition of FAS is updated accordingly due to this additional exclusion.
		
18-Oct-2018	Prior to Final DBL	
Definition of adverse events of special interest updated for hyperkalemia and renal dysfunction.
 
Updates in notable vital signs.
 
Medical history date imputation added.
 
Precision added for CM end date imputation.
 
Clarification for the medications collected after end of study visit.
 
Updates in wording terms used for the duration of treatment and the total exposure to study drug.
 
Updates in clinically notable laboratory parameter definition and adding of imputation rule.
 
Updated 'Change to protocol specified analyses' section.
 
Precision added for the analysis of patients permanently discontinued from study drug, due to any reasons, at any time during the study.
	Amendment 4	
2.8.8.1
 
2.8.4.2
 
4.1.4
 
5.1.3.1
 
2.4.2
 
2.4.1
 
2.8.3
 
4
 
1.2.5

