## 2.2 Analysis sets

The following populations will be used for the statistical analyses:

- Screened set (SCR) – All patients who signed the informed consent. The SCR includes only unique screened patients.
- Randomized Population (RAN) will consist of all patients randomized.
- The full analysis set (FAS) will consist of all randomized patients with the exception of those patients who have inadvertently been randomized into the study. In addition, patients not starting treatment within protocol specified windows will be excluded from FAS. Following the intent-to-treat principle, patients will be analyzed according to the treatment to which they were assigned at randomization.
- The Safety Population (SAF) will consist of all randomized patients who received at least one dose of study drug with the exception of those patients who have inadvertently been randomized into the study. Patients will be analyzed according to treatment actually received. The safety population will be used for the analyses of safety variables.

The protocol deviation codes leading to exclusion from the analysis sets defined above are presented in the section 4.5 Rule of exclusion criteria of analysis sets.

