### **2.5.4 Supportive analyses**

In addition to the primary analysis, a supportive analysis will be carried out, based on evaluable patients in the SAF population where patients with administrative discontinuations (non-AE or non-death reasons) will be considered as non-evaluable, and thus excluded.

As a further supportive analysis, the primary analysis, will be repeated using the FAS population instead of the SAF population,

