### 4 Change to protocol specified analyses

- The definition of the full analysis set (FAS) was updated to exclude patients who have inadvertently been randomized, regardless the study medication intake.
- The definition of the safety analysis set (SAF) was updated to exclude patients who have inadvertently been randomized, regardless the study medication intake.
- Creatinine kinase parameter is not analyzed as the data have not been collected.

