### 5.5 Rule of exclusion criteria of analysis sets

#### Table 5-1 Protocol deviations that cause subjects to be excluded

The table below shows the selected PDs leading to exclusion of the subject from analysis:

Check condition	Protocol Deviation ID (DVSPID)	Description used to Report PDs to HA/IRBs (DVTERM)	PD category - text description (DVDECOD)	Exclusion form analysis
No informed consent signature.	INCL01	No informed consent signature.	SELECTION CRITERIA NOT MET	Exclude from all analysis
Patient randomized but no study medication taken.	TRT04	Patient randomized (who have completed Randomization Visit) but no study medication taken.	TREATMENT DEVIATION	Exclude from SAF analysis
Patient was randomized in error but did NOT receive any study medication.	*OTH10	Patient was randomized in error but did NOT receive any study medication.	OTHER	Exclude from FAS and SAF analysis
Not Hospitalized due to acute decompensated HF episode (ADHF primary diagnosis), including signs and symptoms evaluation at admission.	*INCL03	Not Hospitalized due to acute decompensated HF episode (ADHF primary diagnosis), including signs and symptoms evaluation at admission.	SELECTION CRITERIA NOT MET	Exclude from FAS and SAF analysis
Patient not starting treatment within protocol specified windows.	OTH13	Patient not starting treatment within protocol specified windows	OTHER	Exclude from FAS analysis

\*Subjects with PDs INCL03 and/or OTH10 are considered to have been inadvertently randomized into the study.

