**Table 5-2 Subject classification**

Analysis Set	PD ID that cause subjects to be excluded	Non-PD criteria that cause subjects to be excluded
RAN	INCL01	Patients that did not sign ICF
FAS	INCL01, OTH10, INCL03, OTH13	
Patients that did not sign ICF
 
Patient was randomized in error but did NOT receive any study medication.
 
Patients not hospitalized for acute decompensated heart failure as primary diagnosis (not the same population)
 
Patient not starting treatment within protocol specified windows.

SAF	INCL01, TRT04, OTH10, INCL03	
Patients that did not sign ICF
 
Patient randomized but no study medication taken
 
Patient was randomized in error but did NOT receive any study medication.
 
Patients not hospitalized for acute decompensated heart failure as primary diagnosis (not the same population)

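### The only endpoint analysis by assigned arm (FAS, primary endpoint only) drops patients who missed arm-specific start windows, and the secondary endpoints have no assigned-arm analysis

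*SAP*

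**What the plan says.** - **Primary risk ratio (SAP 2.5.2).** "The above analyses will be performed based on SAF; patients will be analyzed according to treatment actually received". The actual stratum replaces the randomised one. Protocol 9.4.2 also names the SAF.
- **SAF (SAP 2.2, Tables 5-1 and 5-2).** At least one dose is required. Deviation TRT04, "Patient randomized (who have completed Randomization Visit) but no study medication taken", removes a patient from the SAF only.
- **Secondary endpoints (SAP 2.8, 5.4.2).** They are analysed as the primary endpoint is, with references to 2.5.2 and 5.4.1. Both of those sections name the SAF.
- **FAS repeat (SAP 2.5.4).** "As a further supportive analysis, the primary analysis, will be repeated using the FAS population instead of the SAF population". Nothing similar is stated for the secondary endpoints.
- **FAS definition (SAP 2.2).** Patients are grouped as assigned, under the intent-to-treat principle, but "In addition, patients not starting treatment within protocol specified windows will be excluded from FAS". The FAS exclusion codes in Table 5-2 are "INCL01, OTH10, INCL03, OTH13", where OTH13 is the start-window deviation. The document history says of OTH13: "Patients with this PD to be excluded from FAS and included in SAF".
- **Protocol FAS (Protocol 9.1).** All randomised patients, "with the exception of those patients who have not received study drug, but have been inadvertently randomized into the study". There is no window criterion.
- **Listed changes (SAP 4).** "The definition of the full analysis set (FAS) was updated to exclude patients who have inadvertently been randomized, regardless the study medication intake". The OTH13 exclusion is not listed there.
- **Start windows (Protocol 3.1).** Pre-discharge: 7 days from randomisation. Post-discharge: 2 weeks from discharge, or days 12 to 21 from randomisation if the stay is prolonged.

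**The concern.** What is randomised is when LCZ696 is started, and the 10-week clock runs from randomisation. A patient who never starts, or starts outside the window, is part of the result of the assigned strategy. Non-start need not be random: Protocol 3.6 bars initiation at potassium above 5.4 mmol/L or until systolic pressure reaches 110 mmHg, the windows differ by arm, and allocation is open.

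Each planned analysis has a different hole. The SAF loses never-dosed patients. It keeps late starters, but grouping by treatment received may move one to the other arm. The FAS repeat restores assigned groups but drops out-of-window patients, on a criterion that arises after randomisation and differs by arm. That does not fit its intent-to-treat label. For the secondary endpoints, nothing is planned by assigned arm.

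SAP 5.4.1 states that no test will be performed. The estimates are therefore the main result, and the patients they describe matter correspondingly more.

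**Working it through.** **Step 1. Reproduce the plan's figure.** Inputs: 1000 patients (SAP 3), 1:1 allocation, so 500 per arm; 80% success in both arms. SE(log RR) = sqrt[(1−p1)/(p1·n1) + (1−p0)/(p0·n0)] = sqrt(0.2/400 + 0.2/400) = 0.0316. The CI is exp(±1.96 × 0.0316) = 0.940 to 1.064. SAP 3 states 1.00 (0.94, 1.06), so the method matches.

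**Step 2. Who is kept, by planned endpoint analysis.**

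| Analysis | Endpoints | Grouping | Never dosed (TRT04) | Late starters (OTH13) |
|---|---|---|---|---|
| SAF | primary and secondary | as treated | out | in, possibly in the other arm |
| FAS repeat | primary only | as assigned | in, on the better reading | out |

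The better reading is that TRT04 excludes from the SAF only, that randomisation in error without dosing has its own code (OTH10), and that OTH13 patients are said to be in the SAF, hence dosed. Taken literally, however, SAP 2.2 and the FAS row of Table 5-2 describe patients who did not start within the windows, and that also fits someone who never started.

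**Step 3. Effect of never-dosed patients.** Let f be the share never dosed. Count them as failures in the assigned arm and assume no arm switching. Each arm's success rate is multiplied by (1−f), so

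RR(assigned) = RR(SAF) × (1−fPre)/(1−fPost).

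All f values are assumptions, as is the 90% success rate for a dose-maintenance endpoint.

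| fPre / fPost | Success if dosed | SAF RR (95% CI) | Assigned-arm RR (95% CI) |
|---|---|---|---|
| 1% / 5% | 80% | 1.000 (0.939, 1.065) | 1.042 (0.975, 1.114) |
| 1% / 3% | 80% | 1.000 (0.939, 1.065) | 1.021 (0.956, 1.089) |
| 5% / 5% | 80% | 1.000 (0.938, 1.066) | 1.000 (0.933, 1.072) |
| 5% / 1% | 80% | 1.000 (0.939, 1.065) | 0.960 (0.898, 1.026) |
| 1% / 5% | 90% | 1.000 (0.959, 1.043) | 1.042 (0.994, 1.093) |

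First row in counts: 396/495 against 380/475 in the SAF; 396/500 against 380/500 as assigned. At 80% success the shift of 0.042 is about two-thirds of the upper half-width of the CI; at 90% it is about equal to it. For the primary endpoint the FAS repeat would show this shift on the better reading. For the secondary endpoints no planned analysis would.

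**Step 4. At the plan's own trigger.** SAP 2.3 repeats the baseline tables if SAF and RAN differ by more than 10 patients. Eleven never-dosed patients, all in one arm, give 500/489 = 1.022 or 489/500 = 0.978.

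**Step 5. Late starters.** Assume 5 Pre and 25 Post late starters, all dosed, none regrouped, 50% success among them and 80% otherwise. The FAS gives 396/495 against 380/475 = 1.000. The SAF gives 398.5/500 against 392.5/500 = 1.015. This is the difference between two planned results for the primary endpoint, so it would be visible.

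**Step 6. As-treated grouping.** Suppose k of 500 patients assigned to Post are counted as Pre, with success s among them and an assigned-arm RR of 1.00. Then RR = [(400+sk)/(500+k)] / [(400−sk)/(500−k)]. For k = 25 this is 0.963 at s = 50% and 1.019 at s = 95%.

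**The case against.** The strongest reply is that this is a tolerability study. The protocol itself chose the SAF, places up-titration among the safety assessments, describes its purpose as exploratory and assesses no efficacy. A dosed denominator is a disclosed and reasonable choice for that question. This stands, and it is why the SAF analysis should remain primary.

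Three stronger readings are tempting and are not supported:

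- *A reader might infer that late starters vanish from every endpoint analysis.* They do not. The document history and Table 5-2 place OTH13 patients in the SAF, so every SAF endpoint analysis counts them. What is missing is an analysis that keeps them in their assigned arm.
- *A reader might infer that never-dosed patients are lost for the primary endpoint too.* On the better reading of the codes they stay in the FAS, and the repeat shows their effect. The literal wording leaves some doubt.
- *A reader might infer that all three secondary endpoints are equally exposed.* A never-dosed patient cannot discontinue study drug, so a dosed denominator is natural for discontinuation due to adverse events. The gap lies mainly in the two dose-maintenance endpoints.

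The plan also has safeguards: baseline tables repeated on the SAF (2.3), disposition with reasons (2.3.1), time from randomisation to first dose of each level (2.4.1), and adverse events since randomisation in the FAS (2.8.1). The last is an assigned-arm tolerability analysis, but it carries the same OTH13 exclusion. None of them re-estimates an endpoint.

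One could argue that analysing the secondary endpoints identically brings in the FAS repeat. The cross-references go to 2.5.2 and 5.4.1, not to 2.5.4. If the repeat was intended, one sentence would settle it.

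**Conclusion.** The point holds in two parts: (a) the OTH13 exclusion sits in the only assigned-arm endpoint analysis, against that set's stated principle and beyond the protocol's definition; (b) the secondary endpoints, chiefly the two on dose maintenance, have no assigned-arm analysis. It should be fixed.

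The size is conditional. Under the assumptions in the working, each one-point difference between arms in the never-dosed share moves the risk ratio by about 1%, and equal shares leave it unchanged. The documents give no non-start, late-start or switching rates. Protocol section 4 expects about 1000 patients, the number to be randomised, in the primary analysis. A reader might infer a bias of known direction, or a result at risk; the documents support neither. With no test planned, no significance decision is affected.

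The absence of OTH13 from SAP section 4 is clerical, since the document history discloses the change.

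**What to change.** 1. Keep the SAF analysis as primary.
2. Remove OTH13 from the FAS exclusions in SAP 2.2 and Tables 5-1 and 5-2, and state there that TRT04 patients stay in the FAS. The adverse-event analysis since randomisation benefits as well.
3. Extend the FAS repeat in SAP 2.5.4 to the secondary endpoints, by assigned arm and randomised stratum. Count never-starters as failures for up-titration and dose maintenance; show them separately for discontinuation due to adverse events.
4. Tabulate never-starters and late starters by assigned arm, with reasons, beside the disposition table in SAP 2.3.1.

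A separate analysis of all randomised patients is not needed. It would bring back those randomised in error (OTH10) or not hospitalised for the qualifying event (INCL03), whom the SAP excludes on purpose.

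The cost is SAP wording and a few tables from data already collected. Success rates in the repeat will be slightly lower: with 1% and 5% never dosed, 0.80 × 0.99 = 79.2% and 0.80 × 0.95 = 76.0% instead of 80%. A second estimate will need explaining beside the SAF result.

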### 2.1.1 General definitions

In this study, patients are randomized to two Treatment groups:

- Pre-discharge initiation of LCZ696 treatment
- Post-discharge initiation of LCZ696 treatment

Thus *study treatment* in this document will refer to Pre-discharge and Post-discharge. *Study drug* will refer to LCZ696 film-coated tablets at doses of 50 mg, 100 mg, and 200 mg. *Treatment actually received* will refer to the *actual* treatment group, rather than the *randomized* treatment group.

The terms *date of first administration of study drug/treatment* and *date of last administration of study drug/treatment* are the first and last reported dates of administration of LCZ696 reported in the Drug Administration Record page of the eCRF.

The term *Study Day* in this document relates to the Analysis Relative Day, Relative Start Day or Relative End Day as applicable. *Study Day* is defined relative to the analysis reference date, which is the date of randomization; it is the number of days from the reference date to the analysis date. For all dates on or after the analysis reference date, the study day is the difference to the analysis reference date plus one day (ie for date  $\geq$  reference date, study day = date - reference date + 1); for any dates prior to the analysis reference date, the study day is simply the difference to the reference date (ie for date  $<$  reference date, study day = date - reference date). Thus the Subject Reference Start Date is designated as Study Day 1, while the date directly prior to the reference date is defined as Study Day -1 (there is no Study Day 0).

The *baseline* value for any analysis variable in general is defined as the value measured at Visit 101 (Randomization) for all analyses except when a specific definition or reason is provided. For information which is not collected at Visit 101, e.g. physical exam, demography, medical history, local laboratory assessment, etc., the information collected at Visit 1 will be used for *baseline* evaluations.

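### The primary analysis groups patients by actual rather than randomised initiation, with no stated rule, and no planned analysis keeps every dosed patient in the randomised arm

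*SAP*

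**What the plan says.** SAP 2.5.1 places the primary endpoint in the SAF, and SAP 2.5.2 adds that "patients will be analyzed according to treatment actually received, as well as the actual stratum (rather than randomized stratum". SAP 2.1.1 sets the terms: "Thus *study treatment* in this document will refer to Pre-discharge and Post-discharge", and "Treatment actually received* will refer to the *actual* treatment group, rather than the *randomized* treatment group". Neither section says how the actual group is derived from the data. Protocol 5.2 separates the arms by whether the first dose comes before or after discharge. Protocol 9.1 already groups the SAF as received.

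SAP 2.5.4 has two supportive analyses. One stays in the SAF and leaves out administrative discontinuations. In the other, "the primary analysis, will be repeated using the FAS population instead of the SAF population". The FAS goes by randomised arm, but under SAP 2.2 "patients not starting treatment within protocol specified windows will be excluded from FAS". The deviation code is OTH13, added in SAP Amendment 3: "Patients with this PD to be excluded from FAS and included in SAF". SAP Table 5-2 agrees: the FAS exclusion codes are "INCL01, OTH10, INCL03, OTH13" and the SAF codes are "INCL01, TRT04, OTH10, INCL03".

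SAP 2.8 analyses the secondary endpoints in the same way as the primary one. The FAS rerun is specified for the primary analysis only.

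**The concern.** The objective compares two initiation strategies, and both arms take the same drug. For this endpoint, as-treated grouping therefore corrects no drug misallocation. It only moves patients according to something that happened after randomisation. Failing to start before discharge is a result of the Pre strategy, so the comparison should carry it in the Pre arm.

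The move is also lopsided. A Post-assigned patient who starts late is still Post, and becomes Pre only if dosed too early in hospital. A Pre-assigned patient who starts late can become Post.

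The direction could favour Pre. Protocol 3.6 bars starting LCZ696 below a systolic pressure of 110 mmHg or above a potassium of 5.4 mmol/L. Protocol 5.5.4 bases up-titration on hypotension, renal or hepatic impairment and hyperkalaemia. If these problems delay the first dose, the patients leaving Pre would tend to be those less likely to reach target.

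**Working it through.** **Step 1. Reproduce the planned precision.** Inputs: about 1000 patients (SAP 3), 1:1 allocation (SAP 1.1), so 500 per arm, and the success rates in the SAP 3 table. Formula, unstratified: exp(ln RR ± 1.96 × √[(1−p1)/(n1·p1) + (1−p2)/(n2·p2)]).

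- 80% in both arms: √(0.2/400 + 0.2/400) = 0.0316, giving 1.000 (0.940, 1.064). The SAP states 1.00 (0.94, 1.06).
- Post 80%, Pre 75%: √(0.25/375 + 0.2/400) = 0.0342, giving 0.938 (0.877, 1.002). The SAP states 0.94 (0.88, 1.00).

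**Step 2. Trace each dosed patient.** Windows are from protocol 3.1, and the actual group is read as start before or after discharge.

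| Assigned | First dose | Primary (SAF) | Supportive (FAS) |
|---|---|---|---|
| Pre | in hospital, by day 7 and at least 12 h before discharge | Pre | Pre |
| Pre | in hospital, after day 7 | Pre | dropped |
| Pre | after discharge, by day 7 | Post | Pre, unless the 12 h limit is coded as a window |
| Pre | after discharge, after day 7 | Post | dropped |
| Post | day 1–14 after discharge | Post | Post |
| Post | later than 14 days after discharge | Post | dropped |
| Post | in hospital, day 12–21, prolonged stay | Post under protocol 3.1; SAP silent | Post |

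Only the fourth row is counted against Pre in neither analysis. The third row is lost to Pre in the primary analysis only.

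**Step 3. When would a slip occur?** Randomisation may be as late as 48 h before planned discharge, the ACEI washout is 36 h, and the first dose is due at least 12 h before discharge. An ACEI patient randomised at the limit who has just taken an ACEI dose has 48 − 36 − 12 = 0 h of slack to that limit and 12 h to discharge. A slip here falls at about day 2–3, in the third row.

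**Step 4. Size.** Assumptions, none from the documents: all 500 per arm are dosed; m Pre-assigned patients (1–5%, so 5–25) are first dosed after discharge, with success s of 60–40%.

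- Primary RR = [(500·p1 − m·s)/(500 − m)] / [(500·p2 + m·s)/(500 + m)]
- FAS RR, if all m are OTH13 = [(500·p1 − m·s)/(500 − m)] / p2

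| By randomised arm | m, s | Pre | Post | Primary RR | FAS RR |
|---|---|---|---|---|---|
| 80% v 80%, RR 1.000 | 5, 0.6 | 397/495 | 403/505 | 1.005 | 1.003 |
| | 10, 0.5 | 395/490 | 405/510 | 1.015 | 1.008 |
| | 25, 0.4 | 390/475 | 410/525 | 1.051 (0.988, 1.118) | 1.026 |
| Pre 75% v Post 80%, RR 0.938 | 5, 0.6 | 372/495 | 403/505 | 0.942 | 0.939 |
| | 10, 0.5 | 370/490 | 405/510 | 0.951 (0.889, 1.017) | 0.944 |
| | 25, 0.4 | 365/475 | 410/525 | 0.984 (0.920, 1.052) | 0.961 |

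In the second block the deficit is 1 − 0.9375 = 0.0625. The shifts of 0.0042, 0.0134 and 0.0465 hide 7%, 21% and 74% of it.

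If the late starters succeed as often as their own arm (m = 25, s = 0.75), the primary RR is 0.940, a shift of 0.003. With 80% throughout, it stays at 1.000. The FAS column is an upper bound: patients dosed by day 7 normally stay Pre there and cause no shift.

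**The case against.** **The SAP never says that the actual group means start before or after discharge.** This stands. Protocol 5.5.2 ties each medication number to a treatment group and a dose level, so a Pre patient taking Pre-labelled kits at home might remain Pre. The SAP introduction also refers to dataset specifications that are not in the text. A reader might infer that regrouping by start date is certain. The documents make it the natural reading, but no more than that.

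**The tight timetable does not feed the gap in both analyses.** This stands too. The zero-slack case slips at about day 2–3, and the only Pre limit in protocol 3.1's withdrawal list is 7 days. The FAS would normally keep that patient as Pre. Being missed by both analyses takes a first dose that is both after discharge and after day 7, and protocol 3.1 says a patient not treated by then should be withdrawn. It would be wrong to infer that the FAS loses every late starter.

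**The direction is not shown.** Every patient met the blood pressure and potassium limits at randomisation. One who then worsens may stay in hospital, and a first dose there after day 7 still counts as Pre in the primary analysis. Slips due to an early discharge or washout timing need not predict poor titration. Overlapping reasons make a tilt towards Pre plausible; the documents do not establish it.

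**The trial only estimates.** SAP 5.4.1 plans no test, so no error rate is affected. As-received grouping was also set in protocol 9.1, for an endpoint the protocol places under safety. Neither point gives a reason to regroup after randomisation when the comparison is between strategies.

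**Conclusion.** The point holds as a gap in the rules. The primary comparison uses an actual group defined only by time of initiation, with no derivation rule. On the natural reading it moves Pre-assigned patients first dosed after discharge into Post. The FAS restores those dosed by day 7, unless the 12 h limit is coded as a window, and drops the rest. No planned analysis of the primary endpoint keeps every dosed patient in the randomised arm.

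Under the assumed 1–5% slip and 60–40% success, the risk ratio moves by about 0.004 to 0.05. The low end is negligible beside a half-width of about 0.06; the high end is close to it. Hiding 74% of a deficit is the worst corner of that range and should not be read as expected. A reader might also infer that the reported result will be biased towards Pre. That would need a slip rate and a success rate that the documents do not give.

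**What to change.** - In SAP 2.5.2 and 2.8, analyse the primary and secondary endpoints in the SAF by randomised arm, OTH13 patients included. Keep the actual stratum, which is a pre-admission attribute. List this in SAP section 4 as a change from protocol 9.1.
- Keep the as-treated version as supportive, with a rule in SAP 2.1.1. A first dose inside the assigned arm's protocol 3.1 window keeps that arm, so day 12–21 in-hospital Post starts remain Post. Otherwise the patient is Pre if dosed before actual discharge and Post if dosed after. State whether a home start by day 7 counts as inside the Pre window.
- Report, per randomised arm, the number whose actual arm differs, with their success rate, and the number randomised but never dosed. The never-dosed are excluded from the SAF (TRT04), so this change does not recover them.
- If the actual group is already set to the randomised arm, correct the wording in SAP 2.1.1 and 2.5.2 instead.

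Adverse event tables can stay by actual start. The cost is one arm variable in the primary and secondary tables, one supportive rerun, one count table and one line in SAP section 4. Randomised arm and first-dose dates are already recorded.
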